dependable guide for robotic resection. Additional hypotheses are that there will be strong agreement between surgeons on what has positive fluorescence, surgeons will find the folate imaging useful during resection and the procedure will be safe.

For advanced RCC (stage III-IV), folate imaging offers a better chance of complete resection than other treatment options currently available. While level-1 evidence within the literature shows LND in stage I-II RCC has no therapeutic benefit, its role in Stage III-IV disease may show some benefit (Blom 2009). Some groups advocate risk-stratifying of RCC using intraoperative frozen section analysis, which adds considerable cost and time to the surgery.

Intraoperative imaging of FR could improve selection for LNDs and provide real time guidance for the surgical template used. Overall, this will be the first study to use folate targeted intraoperative imaging of RCC to improve clinical outcomes. Data obtained from the proposed pilot study will help develop future protocols with large sample sizes and accurately estimate sensitivity, specificity, positive predictive value, and negative predictive value of OTL38.

4 STUDY OBJECTIVES

Primary

- To explore the use of OTL38 and fluorescence imaging to detect RCC in partial nephrectomy at the margins of resection, and in lymph node(s) or other metastases during radical nephrectomy.

Secondary

To assess the specificity of tumor fluorescence obtained using OTL38 with FR α + renal cell carcinoma cancer lesions detected via immunohistochemistry

- To assess the agreement between fluorescence imaging using OTL28 and FR α by immunohistochemistry
- To assess the agreement between fluorescence imaging using OTL38 and visual/tactile assessments
- To assess the pattern of (lymph) nodal spread during radical nephrectomy
- To assess the degree of agreement of (lymph) nodal and primary tumor fluorescence during radical nephrectomy
- To assess the detection of RCC in primary tumor in situ during radical nephrectomy
- To assess inter-observer variations of tumor fluorescence images captured during surgery
- To assess physician rated usefulness of intra-operative fluorescence imaging- Likert scale questionnaire ([Appendix A](#))
- To assess the safety of OTL38 (perioperative, 1-month)- Vital signs, hematology, chemistry, and adverse events (NCI-CTCAE v4.0)

5 RISKS AND BENEFITS OF OTL38

5.1.1 Risks

The issues of possible concerns with the use of the OTL38 and the imaging system are:

- Presence of an imaging system in the operating room
- Phototoxicity or thermal damage from the light source
- Nonspecific localization of OTL38
- Failure of OTL38 to bind to receptors
- Fading of the chromophore (photobleaching)
- Inability to excite the dye in OTL38 or to record emission
- Adverse events suggestive of hypersensitivity

5.1.1.1 *Imaging system*

The presence of an imaging system in the operating room is not novel and should not create a problem with maintaining a sterile field. In this case, the camera system will be used for intra-operative imaging prior to surgical resection to record the localization of tumors, and post-resection to document the visualization of any residual tumor. As such, it need not be intrusive during the procedure. Standard operating room procedures to ensure a sterile milieu, including appropriate draping of the imaging system, will be employed.

There is a potential for phototoxicity or thermal damage from any light source. The degree of risk is related to the power of the light, the duration of exposure, and the temperature of the light source near the patient. The maximum temperature and irradiance for the imaging system are well within established safety limits. Controls will be in place to ensure that the exposure to the imaging system is limited to that is necessary to identify the tumor lesions and capture images.

Like all chromophores (fluorophores), excitation by appropriate wavelength of light will result in molecular activation resulting in a different wavelength of light being emitted. This is an active process that changes the excitability of the molecule potentially leading to photobleaching. Since white light contains all wavelengths of light, extended room light exposure could lead to bleaching. Exposure to the excitation light source will be limited during the procedure. According to van Dam et al. (2011), the initial images can be captured in a mean time of 10 minutes (4-36 minutes), and tumor-specific fluorescence can be detected for up to 8 hours. The risk that the camera system will not excite the OTL38 dye or record an image after emission is minimal.

5.1.1.2 *OTL38*

Intravenous infusion over 60 min of 0.025 and 0.05 mg/kg OTL38 in a total volume of 220 ml 5% dextrose (D5W) to healthy volunteers was associated with mild adverse events that did not require any intervention, were not considered to be clinically significant, and there appeared to be no relationship to an increase in dose.

5.1.2 Benefits

The potential benefits of OTL38 imaging are:

- Improved staging of the tumor
- Removal of more lesions
- Added assurance of clean margins to excised tumors.

In a preliminary study of ovarian cancer by van Dam et al ([Van Dam 2011](#)), significantly more lesions were detected by surgeons using Folate-FITC than with visual observation alone (34 vs. 7; $p < 0.001$). Lesions that were as small as 1 mm could be detected and removed. This resulted in better staging of patients as more lesions could be visualized but, more importantly, it resulted in greater tumor debulking. Since the degree of tumor removal directly affects the prognosis, this was a large potential benefit. This would need to be studied with OTL38. Use of OTL38 would not change the surgeon's option to remove additional tissue because of impressions based on experience, visualization, or tactile senses.

6 ELIGIBILITY CRITERIA

6.1 Inclusion criteria for localized RCC treated with partial nephrectomy

To be considered eligible to participate in this study, a patient must meet all the inclusion criteria listed below:

- ≥ 18 years of age.
- Have primary or suspected diagnosis of RCC, with presence of cT1-2 renal mass by diagnostic CT assessment.
- Scheduled for partial nephrectomy of renal mass.
- Expected survival of at least 3 months.
- Written informed consent available.
- ECOG ≤ 1 (**Appendix G**).
- Negative serum or urine pregnancy test within 24 hours for females of child bearing age
- Recovered from toxicity of any prior therapy to \geq grade 1.

6.2 Inclusion criteria for advanced RCC treated with radical nephrectomy

To be considered eligible to participate in this study, a patient must meet all the inclusion criteria listed below:

- ≥ 18 years of age.
- Have pathologic or suspected diagnosis of RCC with presence of cT1-4 renal mass and evidence of nodal or metastatic involvement by diagnostic CT assessment
- Scheduled for radical nephrectomy and lymph node dissection.
- Expected survival of at least 3 months.
- ECOG ≤ 2 .
- Negative serum or urine pregnancy test within 24 hours for females of child bearing age.
- Recovered from toxicity of any prior therapy to \geq grade 1
- Written informed consent available.

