6.3 Exclusion criteria for both localized and advanced RCC

- History of any anaphylactic reaction, any severe allergy, or any allergy to folate.
- Brain metastases
- Baseline GFR < 50 mL/min/1.73m²)
- Hepatic toxicity ≥ Grade 2 (using CTCAE version 4 standard definitions).
- Participation in another investigational drug trial either concurrently or 30 days prior to surgery
- Any medical condition that in the opinion of the investigators could potentially jeopardize the safety of the patient, limit the patient's ability to complete the study, and/or compromise the objectives of the study.
- Known sensitivity to fluorescent light

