7 PATIENT REGISTRATION

Patient enrollment will take place over 24 months at a single institution-Indiana University Simon Cancer Center (IUSCC)/Indiana University Hospital (IUH).

All patients will be registered with the Indiana University (IU) Department of Urology. Regulatory files will be maintained by the Department of Urology. Applicable regulatory documents must be completed and on file prior to registration of any patients. Potential patients will be identified in the Urology clinic or by physician referrals. Patients who appear to be eligible for this trial will undergo the Informed Consent Process and be screened for eligibility utilizing the Eligibility Criteria. Individual patient registration will be done in the OnCore[®] database. The original signed Institutional Review Board (IRB) approved Informed Consent Document and completed eligibility checklist will be stored in the following location:

Indiana University Medical Center
Indiana Cancer Pavilion
Urology Clinic, 3rd floor
[name]
[name]

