8.3 Assessments by visit

8.3.1 Screening (Day -90 to Day -1):

- Informed consent: investigators or their designees will discuss with subjects the nature of the study, its requirements, risks, and restrictions to obtain informed consent for participation in the study. Subjects should have sufficient time to review the study information and consent form and to ask any questions necessary to make an informed decision regarding their participation in the study. Written informed consent is to be obtained before any other study-specific procedure.
- Eligibility criteria: make sure patient meets study eligibility criteria.
- Demographics
- Medical history: includes past medical history, past surgical history, allergies and any ongoing medical conditions
- Medication history: all medications noted in patients record at time of screening
- Physical examination: including height, weight, vital signs (blood pressures, heart rate, respiratory rate, and temperature). The extent of the physical examination is determined by the investigator (or designee) and is based on clinical relevance to the subject's medical history and scheduled surgical procedure as per standard medical/surgical care.
- Blood samples: complete blood count with differential (CBC w/ diff) and basic metabolic panel (Na, K, Cl, Mg, Ca, BUN, creatinine), and serum pregnancy for women of childbearing age

8.3.2 Surgery (Day 0):

8.3.2.1 Pre-surgery:

- Eligibility criteria: ensure subject continues to meet study eligibility
- Medical history: capture additional medical history since screening
- Concomitant medications: record medications taken since screening through day of surgery. All preoperative medications (this does not include normal saline or other routine maintenance intravenous fluids) will also be recorded.
- Urine pregnancy test: for women of childbearing age
- Vital signs (blood pressures, heart rate, respiratory rate, and temperature): will be taken at baseline (up to 30 minutes prior to infusion), approximately every 15 minutes during infusion (blood pressure and pulse rate), and then approximately every hour after infusion until surgery is initiated. During and post-surgery these will be recorded per institutional practice.
- Study drug administration:
 - A single dose of anti-histamine (diphenhydramine 25 mg IV) will be administered prior to the study drug.

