16 ADVERSE EVENTS

16.1 Definitions of Adverse Events

16.1.1 Adverse Event

An adverse event (AE) is defined as any untoward medical occurrence associated with the use of a drug in humans, whether or not considered drug related. An adverse event can be any unfavorable and unintended sign (e.g. an abnormal laboratory finding), symptom, or disease temporarily associated with the use of a drug, without any judgment about causality. Adverse events will be graded according to the NCI Common Toxicity Criteria, Version 4.0 (**Appendix F**).

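### The prior-therapy toxicity criterion in 6.1 and 6.2 carries the wrong inequality sign: read literally, unresolved non-hepatic toxicity of grade 2 or higher meets it, although grade 1 or better was evidently intended

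*Combined protocol and SAP*

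**What the plan says.** Section 6.2 (radical nephrectomy arm) states that "a patient must meet all the inclusion criteria listed below", and section 6.1 (partial nephrectomy arm) has the same lead-in. Both lists then contain "Recovered from toxicity of any prior therapy to \geq grade 1". In the extracted text this line shows a raw token for the greater-or-equal sign.

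Three other places bear on how to read it:

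- Section 6.3, which applies to both arms, excludes "Hepatic toxicity ≥ Grade 2 (using CTCAE version 4 standard definitions"). It also excludes a baseline GFR below 50 and "Any medical condition that in the opinion of the investigators could potentially jeopardize the safety of the patient".
- Section 16.1.1 says of events on study: "Adverse events will be graded according to the NCI Common Toxicity Criteria, Version 4.0".
- Section 7 requires a filed eligibility checklist, and the day 0 instructions in section 8.3 say "Eligibility criteria: ensure subject continues to meet study eligibility".

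No other section states the prior-toxicity rule in the opposite direction, and none defines ≥ grade 1 as grade 1 or better.

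**The concern.** A criterion of this kind normally sets a ceiling on residual toxicity, so that patients enter surgery and receive the study drug without unresolved harm from earlier treatment. With the sign as printed, the literal text sets a floor instead. A patient whose earlier treatment left, say, a grade 3 non-hepatic toxicity would meet it.

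The line is an operative threshold that decides who may be enrolled. Eligibility is assessed at screening and again on day 0. What is at stake is safety at entry for previously treated patients, and an eligibility record that can be audited without staff having to read past a symbol. The radical nephrectomy arm requires nodal or metastatic involvement, and section 3.2 mentions systemic therapies for advanced disease, so prior therapy is plausible there.

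**Working it through.** The plan gives no figure on this point, so the check sets the rules side by side.

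**Inputs**

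1. Criterion as printed, both arms (6.1, 6.2): residual grade ≥ 1.
2. Criterion as evidently intended: residual grade ≤ 1.
3. Direction of the scale: 6.3 excludes hepatic toxicity at grade 2 and above, so within this protocol a higher grade is worse.
4. Hepatic exclusion (6.3): grade ≥ 2 is out.
5. Grades considered: 0 to 4, with 0 taken to mean no residual toxicity. The protocol does not define grade 0, and Appendix F does not reproduce the grading criteria, so this is an assumption.

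**Who meets the rule, by residual grade**

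| Residual grade | Printed sign (≥ 1) | Intended sign (≤ 1) | Hepatic toxicity: printed sign with 6.3 | Hepatic toxicity: intended sign with 6.3 |
|---|---|---|---|---|
| 0 | no | yes | no | yes |
| 1 | yes | yes | yes | yes |
| 2 | yes | no | no | no |
| 3 | yes | no | no | no |
| 4 | yes | no | no | no |

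**Reading the table**

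- For non-hepatic toxicity, the printed sign lets grades 2, 3 and 4 through. The intended sign stops them.
- For hepatic toxicity, 6.3 already removes grades 2 to 4 whichever sign is used. The printed sign with 6.3 leaves only grade 1, which no sensible design would aim for. The intended sign with 6.3 leaves grades 0 and 1, so the two rules agree. This is internal evidence that ≤ was meant.

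**What else could stop a non-hepatic grade 2 to 4 toxicity?** The GFR limit covers renal function. The performance-status limits may catch some severely affected patients indirectly. The remaining safeguard is the investigator-discretion exclusion, which names no grade. Among the toxicities in 6.3, only the hepatic one has a grade cap.

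**Is the sign a reading artefact?** In the same lists, ≥ 18 years and ECOG ≤ 1 (6.1) or ≤ 2 (6.2) came through with distinct and correct signs. The toxicity line carries the greater-or-equal token in both lists. A misread is therefore unlikely, though the extracted text alone cannot exclude it.

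**The case against.** The strongest reply is that the line speaks of having recovered to a grade. Recovery has a direction, so the phrase can be read as recovered at least as far as grade 1, which is the intended rule. This stands as an account of what was meant and of how a single-site surgical team would probably apply it. It does not make the symbol right: the same protocol uses ≥ with grades in its ordinary numerical sense in 6.3.

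A reader might go further than the documents allow in three ways.

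- **That fully recovered patients are barred.** The grade 0 row of the table follows mechanically from the printed sign, but the inference is strained. A patient with no remaining toxicity, or with no prior therapy, is naturally taken to satisfy a criterion about recovery.
- **That the checklist and the day 0 check repeat the error.** Section 7 says only that a "completed eligibility checklist will be stored in the following location", and section 8.3 says only that continued eligibility is to be ensured. The wording of the checklist is not shown, so it may already be correct.
- **That 16.1.1 fixes the scale for this criterion.** That section concerns adverse events associated with use of a drug. The eligibility text that names a grading version is the hepatic exclusion in 6.3, and the direction of the scale rests on that.

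On the symbol itself, the two lines are near-identical and went through the same conversion, so they are not independent confirmations. That is a fair reason to look at the source PDF before amending. It does not outweigh the correct signs in neighbouring lines.

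The discretionary exclusion also stands as real protection. It lowers the chance of harm but leaves the written threshold uncorrected.

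**Conclusion.** The point holds as a minor wording error in a mandatory eligibility threshold. Read literally, the criterion in both arms is met by unresolved non-hepatic toxicity of grade 2 or higher, and no other rule in section 6 stops such toxicity by grade. The intended rule is clear enough that misapplication is unlikely.

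The effect is confined to previously treated patients. The documents give no count of them, so the number affected is unknown and may be zero. The sample size of 20, the sensitivity and specificity analyses, the 70% sensitivity threshold in 12.3 and the adverse event definitions are all unaffected.

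The conclusion assumes that the source PDF shows the same sign as the extracted text, and that prior-therapy toxicity is graded on a scale running in the same direction as the one named in 6.3.

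**What to change.** 1. Confirm the symbol in the source PDF for 6.1 and 6.2.
2. If confirmed, replace ≥ grade 1 with ≤ grade 1, or with the words grade 1 or better, in both sections.
3. Check that the eligibility checklist used for screening and for the day 0 re-check says the same, and correct it only if it does not.

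The cost is one symbol in two criteria, which can go with the next amendment. Accrual does not change if the team already applies the rule as intended.

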6.3 Exclusion criteria for both localized and advanced RCC

- History of any anaphylactic reaction, any severe allergy, or any allergy to folate.
- Brain metastases
- Baseline GFR < 50 mL/min/1.73m²)
- Hepatic toxicity ≥ Grade 2 (using CTCAE version 4 standard definitions).
- Participation in another investigational drug trial either concurrently or 30 days prior to surgery
- Any medical condition that in the opinion of the investigators could potentially jeopardize the safety of the patient, limit the patient's ability to complete the study, and/or compromise the objectives of the study.
- Known sensitivity to fluorescent light

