8.2 Study calendar

Study Procedures ¹²	Screening	Pre-surgery	Surgery	Post-surgery	Hospital Admission	Hospital Discharge	Follow-up Phone Call	Follow-up Appt
	Up to 90 days prior to surgery	Day 0			Days 1-5	Days 2-6	Day 10 (± 3 days)	1 Month (±14 days)
Informed consent	X							
Inclusion/exclusion criteria	X							
Demographics	X							
Medical history ¹	X	X ²						
Physical exam	X							X
Height/weight	X							X ³
Vital signs ⁴	X	X ⁵	X ⁶	X ⁶	X ⁶	X ⁶		X
Urine/serum pregnancy test	X ⁷	X ⁸						
Complete metabolic panel (CMP)								X
Basic metabolic panel (BMP) ⁹	X				X ¹⁰			
CBC w/ diff	X				X ¹⁰			X
Study drug administration ¹¹		X						
Surgery with associated procedures including intra-operative imaging			X					
Tumor ex-vivo sample collection			X					
Pathologic assessment				X				
PI Likert questionnaire				X				
AE assessments		X	X	X	X	X	X	X
ADE assessments			X	X	X	X	X	X
Concomitant medications	X	X ¹	X	X	X	X	X	X

Footnotes:

¹Includes past medical history, past surgical history, allergies and any ongoing medical conditions

²Since screening visit and up to 30 days before surgery

³Weight only

⁴Temperature, blood pressure, respiratory rate and pulse rate

⁵Taken at baseline (up to 30 minutes prior to OTL38 infusion), approximately every 15 minutes during infusion (only blood pressure and pulse rate), and then approximately every hour after infusion until surgery is initiated

⁶Record per institutional practice

⁷Serum pregnancy test for all females of childbearing potential

⁸Urine pregnancy test for all females of childbearing potential

⁹Basic metabolic panel includes Na, K, Cl, Mg, Ca, BUN, creatinine

¹⁰Obtain on day 1 after surgery

¹¹Single dose of anti-histamine (diphenhydramine 25 mg IV) will be administered prior to the study drug; study medication will be administered less than 2 hours prior to the skin incision

¹²Patients from both arms will follow this schedule

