- Concomitant medications: record all postoperative medications (this does not include normal saline or other routine maintenance intravenous fluids)

8.3.3 In-hospital admission (Days 1-5):

- Blood samples: complete blood count w/ differential (CBC w/ diff) and basic metabolic panel (BMP) *on day 1 after surgery*
- Vital signs: recorded per institutional practice
- AE assessment: including hypersensitivity reactions, which could include skin reactions, difficulty breathing, eye or nasal reactions, or gastrointestinal complaints, redness, tenderness, pain, or rash at the injection site or any clinically relevant abnormality (with exception of surgical scars) that was not present at screening.
- ADE assessment: the surgeon will examine the subject to confirm that there are no visible changes to skin (erythema or pigment darkening), tissue or organs related to fluorescence.
- Concomitant medications: record all postoperative medications (this does not include normal saline or other routine maintenance intravenous fluids)

8.3.4 Hospital discharge (Day 2-6):

- Vital signs: recorded per institutional practice
- Review records relating to discharge: date and time that discharge order was written (must occur the same day)
- AE assessment: including hypersensitivity reactions, which could include skin reactions, difficulty breathing, eye or nasal reactions, or gastrointestinal complaints, redness, tenderness, pain, or rash at the injection site or any clinically relevant abnormality (with exception of surgical scars) that was not present at screening.
- ADE assessment: the surgeon will examine the subject to confirm that there are no visible changes to skin (erythema or pigment darkening), tissue or organs related to fluorescence.
- Concomitant medications: record all postoperative medications (this does not include normal saline or other routine maintenance intravenous fluids)

8.3.5 Follow-up phone call (Day 10 [±3 days]):

- AE assessment: including hypersensitivity reactions, which could include skin reactions, difficulty breathing, eye or nasal reactions, or gastrointestinal complaints, redness, tenderness, pain, or rash at the injection site or any clinically relevant abnormality (with exception of surgical scars) that was not present at screening.

- ADE assessment: the surgeon will examine the subject to confirm that there are no visible changes to skin (erythema or pigment darkening), tissue or organs related to fluorescence.

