- Concomitant medications: record any new medications taken since discharge
- A letter will be sent to any subject not contacted after 3 attempts by telephone

8.3.6 Follow-up appointment (1 Month [± 14 days]):

- Physical examination: including weight and vital signs (blood pressures, heart rate, respiratory rate, and temperature). The extent of the physical examination is determined by the investigator (or designee) and is based on clinical relevance to the subject's medical history and scheduled surgical procedure as per standard medical/surgical care.
- Blood samples: complete blood count with differential (CBC w/ diff) and complete metabolic panel (CMP)
- AE assessment: including hypersensitivity reactions, which could include skin reactions, difficulty breathing, eye or nasal reactions, or gastrointestinal complaints, redness, tenderness, pain, or rash at the injection site or any clinically relevant abnormality (with exception of surgical scars) that was not present at screening.
- ADE assessment: the surgeon will examine the subject to confirm that there are no visible changes to skin (erythema or pigment darkening), tissue or organs related to fluorescence.
- Concomitant medications: record any new medications since discharge or follow-up phone call

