9 TOXICITIES TO BE MONITORED

The safety measures included in this study are standard for studies of investigational drugs. Additional monitoring following administration of study drug is due to screening for a hypersensitivity reaction after administration of OTL38 and for any adverse events that might be related to fluorescent imaging.

Any clinically relevant abnormality (with exception of surgical scars) noted after the start of the study medication that was not present at the screening should be recorded as an adverse event (AE).

On Target, LLC will be notified of any serious adverse events (SAEs) that occur and are felt to be due to the investigational drug by the investigators.

More details about AEs and SAEs can be found in Section 15.

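### Hepatic toxicity of grade 2 or higher is an exclusion, but no liver test is required before dosing, so analytes measured only in the 1-month metabolic panel also lack a required screening value

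*Combined protocol and SAP*

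**What the plan says.** Section 6.3, which applies to both arms, excludes "Hepatic toxicity ≥ Grade 2 (using CTCAE version 4 standard definitions").

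Screening is allowed "Up to 90 days prior to surgery" (section 8.2). Its chemistry is given in section 8.3.1 as a "basic metabolic panel (Na, K, Cl, Mg, Ca, BUN, creatinine), and serum pregnancy for women of childbearing age", and the calendar footnote lists the same seven analytes. On day 0, section 8.3.2.1 asks staff to re-confirm eligibility ("Eligibility criteria: ensure subject continues to meet study eligibility"), but the only laboratory test that day is a urine pregnancy test.

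After dosing, day 1 calls for a "complete blood count w/ differential (CBC w/ diff) and basic metabolic panel (BMP") in section 8.3.3. The 1-month visit in section 8.3.6 calls for "Blood samples: complete blood count with differential (CBC w/ diff) and complete metabolic panel (CMP"). The CMP row of the calendar has one entry, at that visit.

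Two safety rules bear on how a 1-month result is handled. Section 16.1.1 states that "An adverse event can be any unfavorable and unintended sign (e.g. an abnormal laboratory finding), symptom, or disease" may count. Section 9 records as an adverse event "Any clinically relevant abnormality (with exception of surgical scars) noted after the start of the study medication that was not present at the screening". Section 12.4 names chemistry within the safety endpoint of both arms.

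**The concern.** A graded exclusion normally has a required measurement behind it. Here, any part of the hepatic grade that depends on a laboratory value cannot be checked from data the protocol requires. Two patients with the same liver status could be handled differently according to what happened to be in their records.

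The safety data inherit the same gap. The section 9 rule turns on whether an abnormality was present at screening. For an analyte first measured by protocol after dosing, the trial's own data cannot answer that question, so a long-standing abnormality might be entered as a new event. This is plausible in arm 2: section 6.2 requires nodal or metastatic involvement and allows for prior therapy, and section 6.3 excludes metastases by site only for the brain.

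**Working it through.** The plan states no figure on this point, so the check sets the laboratory schedule against the criterion and the adverse-event rule.

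**Step 1. Chemistry required at each time (sections 8.2 and 8.3).**

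| Time | Chemistry required |
|---|---|
| Screening, day -90 to day -1 | BMP |
| Day 0, before dosing | none |
| Day 1 | BMP |
| Discharge and day-10 call | none |
| 1 month ± 14 days | CMP |

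The calendar and the visit text agree at every row, so this is not the effect of a badly extracted table.

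**Step 2. Liver tests before dosing.** The BMP lists Na, K, Cl, Mg, Ca, BUN and creatinine: 7 analytes, of which 0 are liver tests. There is 1 scheduled chemistry draw before dosing and it is not a CMP. Over the whole study, 1 of 3 scheduled chemistry draws is a CMP.

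**Step 3. Comparison with the other laboratory-based criteria.** The pregnancy criterion has a required test at screening and again on day 0. The GFR exclusion in section 6.3 can be supported by the creatinine on the screening BMP. The hepatic exclusion has no corresponding required test.

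**Step 4. Baseline for the safety data.** The blood count is scheduled at screening, day 1 and 1 month, so it has a screening comparison. The BMP analytes have a screening value and a day-1 value. An analyte that is on the CMP but not on the BMP has 0 required values before dosing and 1 after. With a month taken as 30 days, that single value falls between day 30 - 14 = 16 and day 30 + 14 = 44.

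**Step 5. Which planned outputs are touched.** Section 12.8 lists laboratory values and marks those outside the normal range. That needs only the value and the range, so it can be produced as planned. Section 12.8 also summarises adverse events and TEAEs. Whether a clinically relevant CMP-only abnormality enters those summaries depends on the section 9 rule, and that is where the missing screening value matters. No change-from-baseline or shift table is planned, so none is lost.

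**The case against.** The strongest reply is that the exclusion does have means of enforcement. Screening requires medical history with ongoing conditions, medication history and a physical examination. Section 7 requires a completed eligibility checklist, day 0 repeats the eligibility check, and section 6.3 has a general exclusion based on investigator judgement. This is a single site with one eligibility process, and no section says the hepatic grade must come from a study-mandated test. All of this stands. A reader might infer that the exclusion is inoperative or that ineligible patients will be enrolled; the documents do not support that. They show only that the protocol does not require the evidence a graded criterion would ordinarily use.

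Second, the section 9 rule covers only clinically relevant abnormalities and refers to presence at screening, not to a laboratory baseline, so history and existing records can inform it. That also stands, which is why the adverse-event consequence is conditional.

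Third, every patient has a nephrectomy and there is no untreated comparison group, so a screening value would not settle whether the drug caused a finding. This is correct. The screening value separates new from old and does no more.

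Fourth, the documents never list the contents of the CMP, which is called complete in section 8.2 and comprehensive in the list of abbreviations. Its inclusion of liver tests is an assumption. The missing baseline, however, applies to whatever the panel contains beyond the BMP.

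**Conclusion.** The mismatch is real and can be read directly from the schedule: a hepatic exclusion at grade 2 or higher, 0 liver tests required before dosing, and 1 CMP in the whole study, at 1 month. Following the protocol exactly leaves the exclusion without a required test and leaves CMP-only analytes without a required screening value.

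Its practical weight is minor. Section 5.1.1.2 describes no hepatic signal among the 23 phase 1a volunteers given OTL38, although they were healthy and not patients with RCC. The primary endpoint and the accuracy analyses do not use these data, and the out-of-range listing is intact.

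A reader might infer that reported adverse-event rates will be distorted by some definite amount. The documents give no frequency of liver abnormality at entry and no rate at which old findings would be classed as new, so no size can be put on that effect. The conclusion rests on the assumption that the CMP includes liver tests. The protocol cites CTCAE version 4 without reproducing it, so how far the hepatic grade depends on laboratory values is also not shown there.

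**What to change.** In sections 8.2 and 8.3.1, add a CMP to the screening blood sample that is already taken, and state that the panel includes liver tests. Keep Mg and the other BMP analytes at screening so that the day-1 BMP retains its comparison. This is a cheap improvement: a minor amendment to two sections and the small laboratory cost of a fuller panel per patient.

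Its limits should be accepted openly. The screening result may be 1 to 90 days old at dosing, and day 0 would still have no chemistry. With a 30-day month, the interval from screening CMP to 1-month CMP would run from 1 + 16 = 17 days to 90 + 44 = 134 days. The added value would show whether a 1-month finding is new, but not what caused it.
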